**Summary of Changes from Previous Version:**

Version #	Version Date	Summary of Revisions Made
1	03Apr2020	
2	19Apr2020	

## STATEMENT OF COMPLIANCE

The trial will be conducted in compliance with the protocol, International Conference on Harmonisation Good Clinical Practice (ICH GCP) and applicable state, local and federal regulatory requirements (United States (US) Code of Federal Regulations (CFR) applicable to clinical studies (45 CFR Part 46, 21 CFR Part 50, 21 CFR Part 56, and/or 21 CFR Part 812). Each engaged institution must have a current Federal-Wide Assurance (FWA) issued by the Office for Human Research Protections (OHRP) and must provide this protocol and the associated informed consent documents and recruitment materials for review and approval by an appropriate Institutional Review Board (IRB) or Ethics Committee (EC) registered with OHRP. Any amendments to the protocol or consent materials must also be approved before implementation. The protocol, informed consent form(s), recruitment materials, and all participant materials will be submitted to the Institutional Review Board (IRB) for review and approval. Approval of both the protocol and the consent form must be obtained before any participant is enrolled. Any amendment to the protocol will require review and approval by the IRB before the changes are implemented to the study. In addition, all changes to the consent form will be IRB-approved; a determination will be made regarding whether a new consent needs to be obtained from participants who provided consent, using a previously approved consent form.

## 1 PROTOCOL SUMMARY

### 1.1 SYNOPSIS

Title:	A Clinical Performance Evaluation of the SARS-COV-2 Direct Antigen Rapid Test "DART"
Study Description:	A rapid point of care bioassay for the detection of virus particles will be compared to the hospital validated RT-PCR detection standard. Nasopharyngeal and saliva samples will be collected along with hospital standard of care collection.
Intended Use	The SARS-CoV-2 DART is a bioassay intended for rapid point-of-care detection of the SARS-CoV-2 virus
Objective	Primary: To validate the performance of SARS-COV-2 DART in a clinical setting
Endpoints:	Primary: Compared to Gold Standard PCR, DART with nasopharyngeal swab will provide agreement with respect to PCR

Study Population:	Samples will be collected in an Emergency Room setting from up to 200 subjects who entered the hospital over concerns about SARS-CoV-2. The goal is to collect a minimum of N=30 confirmed Covid-19 positive subjects and N=30 confirmed Covid-19 negative subjects of comparable ages, genders and races.
Phase:	N/A
Description of Sites/Facilities Enrolling Participants:	Beth Israel Deaconess Medical Center
Study Duration:	The trial is expected to take 1 month
Participant Duration:	Individual participation only includes sample collection

1.2 SCHEMA

Prior to Enrollment

Total up to N=200: Obtain informed consent. Screen potential participants by inclusion and exclusion criteria; document relevant medical history

Enrollment

Covid (+/-)  
Clinical criteria

Time Point

- Perform nasopharyngeal swabs
- One swab will be used for PCR according to hospital protocol
- The second swab will be used for DART antigen test
- Place sample in DART tube in the E25Bio transport media
- Add dipstick
- Collect saliva and serum for future use

**Final Assessments**

Collect readings after 15 and after 30 minutes

## 2 INTRODUCTION

### 2.1 STUDY RATIONALE

The current standard of care for diagnosis of SARS-CoV-2 infection involves sample collection to be prepared and measured via real time-polymerase chain reaction (RT-PCR). This process is often time consuming depending on the level of automation within the laboratory processing the samples. In many cases, sample turn-around times can take hours to several days. A rapid assay that does not require the sophisticated laboratory equipment and techniques could provide a significant advantage to the way practitioners screen and ultimately treat patients.

### 2.2 BACKGROUND

The SARS-CoV-2 Direct Antigen Rapid Test (“DART”) is an immunoassay for point-of-care, qualitative detection of SARS-CoV-2 viral particles/secreted protein in nasopharyngeal swabs from suspected patients with COVID-19 infection. Dipsticks are printed with a monoclonal antibody that binds the signature SARS-CoV-2 viral particles/protein (Test line) and a control antibody (Control line) for quality control. A second monoclonal antibody is attached to gold nanoparticles (conjugate) and quencher buffer, and mixed with the patient samples, though in the near future the final format will contain the dry conjugate. The SARS-CoV-2 viral particles/Spike protein attach to both antibodies resulting in a visual line on the test strip within 15 minutes. Prior experience for detection virus and viral proteins via antibody binding using lateral flow are E25Bio portfolio platform for dengue, Zika and Chikungunya viruses among others.

### 2.3 RISK/BENEFIT ASSESSMENT

#### 2.3.1 KNOWN POTENTIAL RISKS

- Potential risk of False Positive results leading to unnecessary clinical care which may include medications and additional diagnostic tests.
- Potential risk of False Negatives which may delay potential therapeutic care, and in severe cases may delay critical lifesaving care
- Negative results cannot be proven negative

*In both cases, the risks are mitigated by the Inclusion/Exclusion requirement that subjects test positive or negative for Covid-19 via the standard RT-PCR diagnostics.*

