### 5 STUDY POPULATION

#### 5.1 INCLUSION CRITERIA

Up to 200 subjects will be screened, consented, and enrolled to obtain 60 eligible candidates. In order to be eligible to participate in this study, an individual must meet all of the following criteria:

1. Provision of verbal informed consent form
2. Subject is suspected case of COVID-19 by clinical criteria: a patient with acute respiratory tract infection (sudden onset of at least one of the following: cough, fever, shortness of breath, fatigue, decreased appetite, myalgia) AND with no other etiology that fully explains the clinical presentation, with or without a history of close contact with a confirmed or probable COVID-19 case in the last 14 days prior to onset of symptoms.
3. Subject is an appropriate candidate for Nasopharyngeal sample collection
4. Subject is willing to provide nasopharyngeal swab and saliva samples

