## 7 STUDY ASSESSMENTS AND PROCEDURES

### 7.1 STUDY PROCEDURES

All reagents and DART viral transport media will be provided by the sponsor and shipped together. The dipsticks should be kept at Room Temperature until use.

1. Subjects will be approached by research staff to determine if they would be interested in participating in a study that requires an additional sample collection. If willing, then a qualified study team member will conduct the informed consent process with the subject, obtain verbal agreement by subject, document verbal consent of the participant, and provide a copy of the informed consent form information sheet to the participant.
2. Study staff will complete the necessary source document elements and case report forms collecting relevant subject demographic information, eligibility criteria, and medical history. Medical personnel will collect nasopharyngeal swabs (2X samples each), saliva, and serum.
3. One of the swabs will be utilized to conduct the traditional PCR method at the Hospital
4. The second nasopharyngeal swab collected in the 0.4ml viral E25Bio transport media
5. Mix vigorously and let stand until use within the next minutes
6. In a tube provided, apply the 100µl viral transport media
7. Insert dipstick for DART test into the tube.
8. The liquid should be moving up into the tests strip for minimum of 15 min and maximum of 30 minutes.
9. Visually read and interpret the final result as indicated below, two lines= positive. One line=negative and record on form.
10. A second DART swab may be administered if the results of the first swab are not interpretable.
11. Medical staff will collect saliva sample from participant for future use.

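### Section 2.3.1 rests control of false DART results on an RT-PCR eligibility requirement that the protocol does not contain, and nothing shown bars use of the reading for care before PCR returns

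*Protocol*

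**What the plan says.** Section 2.3.1 lists two harms. A false positive could bring needless treatment and further tests. A false negative could hold up treatment, in the worst case treatment on which survival depends. For both it gives a single control: "the risks are mitigated by the Inclusion/Exclusion requirement that subjects test positive or negative for Covid-19 via the standard RT-PCR diagnostics".

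Section 5.1 defines disease status at entry by clinical suspicion: "Subject is suspected case of COVID-19 by clinical criteria". In the schema (1.2), the step before enrolment is "Screen potential participants by inclusion and exclusion criteria; document relevant medical history". The later sampling step includes "One swab will be used for PCR according to hospital protocol", with the other swab going to DART. Section 7.1 step 3 agrees: "One of the swabs will be utilized to conduct the traditional PCR method at the Hospital".

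On timing, the schema says "Collect readings after 15 and after 30 minutes", and section 2.1 says of RT-PCR: "In many cases, sample turn-around times can take hours to several days". On what happens to the DART reading, 7.1 step 9 says only: "Visually read and interpret the final result as indicated below, two lines= positive. One line=negative and record on form".

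**The concern.** The harms listed in 2.3.1 can arise only if someone acts on a DART reading, so the authors regarded that as possible. The setting is an emergency room, and the form records each reading as positive or negative for COVID-19. A review board weighing this risk is told that an eligibility rule controls it.

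If that rule is absent, the board is relying on a safeguard that the study does not have. Staff at the bedside may also hold a result before PCR is back, with no visible instruction on whether they may use it.

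**Working it through.** No calculation applies, because the point does not depend on alpha, power or an effect size. The check sets the relevant sections side by side.

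**1. Is there a PCR requirement among the criteria?**

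| Place | Content | PCR mentioned? |
|---|---|---|
| 5.1, criterion 1 | Verbal consent | No |
| 5.1, criterion 2 | Clinically suspected case | No |
| 5.1, criterion 3 | Suitable for nasopharyngeal sampling | No |
| 5.1, criterion 4 | Willing to give swab and saliva | No |
| 5.2, criterion 1 | Symptoms for 10 days or more, or already recovering | No |
| CRF 13.1 | Consistent symptoms; all criteria met; enrolled | No |

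That is 4 + 1 = 5 criteria, of which 0 mention PCR. The CRF eligibility page has no PCR item either. The PCR result is recorded in CRF 14.3, under assessments and not under screening.

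**2. Could PCR act at entry?** In the schema, the criteria are applied before enrolment and the PCR swab is taken at the later sampling step. In 7.1, consent is step 1, eligibility data and swab collection are step 2, and PCR is step 3. The study PCR swab is taken alongside the DART swab, so its result cannot have been used to admit the subject.

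**3. Would the requirement work if it existed?** A rule that subjects test positive or negative is met by anyone with a valid PCR result. It would not stop a clinician from acting on a false DART reading.

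**4. Where does PCR status matter?** It matters in two places: the synopsis target of at least 30 confirmed positives and 30 confirmed negatives, and the analysis population in 8.3. Both determine which data are counted. Neither governs how a subject is managed.

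**5. Which result comes first?** DART is read at 15 and 30 minutes. Section 2.1 puts PCR, in many cases, at hours to several days. On that general description DART can be known first. This hospital's own turnaround is not stated, so the length of the gap cannot be derived, and it is zero if PCR is back by the first reading.

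**6. Is use of the reading for care barred anywhere?** Section 7.1 step 9 sends the reading to the study form and says no more. Section 2.3.2 expects no benefit to the subject, which suggests research-only use without stating it. The confidentiality and publication clauses (9.1.3, 9.1.9) restrict release to third parties, not to the treating team. No visible section contains a bar.

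**The case against.** The strongest reply is that the sentence in 2.3.1 is a mislabel and that the protection it describes is real. Every subject has hospital PCR, and the study samples are taken alongside standard-of-care collection. The synopsis asks for confirmed positives and negatives. Section 5.1 opens by speaking of obtaining 60 eligible candidates from up to 200 enrolled, which uses the word eligible loosely for a subset defined later. This stands as an explanation of how the sentence arose, and hospital PCR is a genuine backstop. It does not make the sentence correct, and it does not cover the time between the DART reading and the PCR result. The phrase about 60 candidates is a separate wording matter.

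A second reply is that the protocol as a whole points to research-only readings. Participation is limited to sample collection, subjects are offered an additional sampling and not a diagnosis, 7.2.4 attributes adverse events to the swab procedure and not the device, and no section tells staff to report or act on DART. This also stands as context, but none of it is an instruction.

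A third reply is that the consent pages and the manual of procedures mentioned in 9.1.8 are not visible and may contain the bar. That is right, and it limits the second half of the point. It leaves the error in 2.3.1 untouched.

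A reader might infer more than this: that subjects have no protection, that DART will direct care, that the exposed interval can be put in hours, or that the agreement estimates are biased. The documents support none of these. Hospital PCR is planned for all, no section directs care by DART, the local turnaround is not given, and nothing here changes the 2 x 2 table in 8.4.1.

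**Conclusion.** The point holds in a limited form. The only mitigation that 2.3.1 states for false DART results is absent from the eligibility criteria (0 of 5) and from the CRF eligibility page, and the order of procedures means that it could not operate at entry. This part rests on the visible text alone and is certain.

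The protection that does exist is hospital PCR, which may arrive after the DART readings. No visible section bars clinical use of the reading until then. This part assumes that hospital turnaround can exceed 15 to 30 minutes, as 2.1 describes in general, and that the unseen consent material does not already contain a bar.

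The matter could touch each subject with a DART reading: at least 30 + 30 = 60 if the recruitment goal is met, and at most 200. That is a count of subjects for whom the rule is needed, not of expected harms. It is a participant-protection correction that should be made, with no consequence claimed for positive or negative percent agreement or for sample size.

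**What to change.** Make two wording changes.

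- **Section 2.3.1**, replace the mitigation sentence with: *DART readings are for research only and do not guide care; all subjects receive hospital RT-PCR, and management follows PCR and clinical judgement. PCR status is not an eligibility criterion.*
- **Section 7.1, step 9**, add: *The reading is recorded on the study form and is not reported to the treating team or used for clinical management.*

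Clinical judgement needs to be named beside PCR, because section 4.1 accepts that PCR sensitivity falls short of 100% and because care has to proceed before PCR returns. The consent information sheet should be checked to see that it says the same.

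No new data, visit or CRF item is needed. The cost is that staff will hold a reading on which they may not act and must be briefed accordingly. The protocol does not name who reads the dipstick, so the site has to settle that first.

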### 2.3.2 KNOWN POTENTIAL BENEFITS

No potential benefits to the subject are expected as a result of participation in this trial. The benefits to future patients may include a more rapid point-of-care diagnostic test than currently available.

## 3 OBJECTIVES AND ENDPOINTS

OBJECTIVES	ENDPOINTS	JUSTIFICATION FOR ENDPOINTS
Primary		
The primary objective is to confirm performance and validation of the SARS-CoV-2 DART bioassay for rapid detection of infection when using nasopharyngeal swab	Agreement with respect to PCR	Commonly accepted thresholds for antigen lateral flow bioassays

## 4 STUDY DESIGN

### 4.1 OVERALL DESIGN

This trial is a clinical performance validation comparing DART to RT-PCR. The endpoints will be agreement with PCR. We know that the sensitivity of PCR will not reach 100%, but we will use PCR to define positive samples. In addition, routine pathogen screen will be in place for Influenza A and B, Adenovirus, RSV for the Hospital Clia Lab protocols.

### 4.2 SCIENTIFIC RATIONALE FOR STUDY DESIGN

Alternatives to genome detection are critical for front line point of care medical specialists when battling an active epidemic. Lateral flow bioassays are relatively inexpensive to manufacture, easy to store, and easy for front line medical

technicians to use. A test that is comparable and reproducible when compared to Gold Standard RT-PCR will meet these critical needs.

#### 4.3 END OF STUDY DEFINITION

Study Subjects are not expected to participate beyond consent and collection of the nasopharyngeal and saliva samples.

The end of the study is defined as completion of the last procedure shown in the SoA in the trial globally.

### 5 STUDY POPULATION

#### 5.1 INCLUSION CRITERIA

Up to 200 subjects will be screened, consented, and enrolled to obtain 60 eligible candidates. In order to be eligible to participate in this study, an individual must meet all of the following criteria:

1. Provision of verbal informed consent form
2. Subject is suspected case of COVID-19 by clinical criteria: a patient with acute respiratory tract infection (sudden onset of at least one of the following: cough, fever, shortness of breath, fatigue, decreased appetite, myalgia) AND with no other etiology that fully explains the clinical presentation, with or without a history of close contact with a confirmed or probable COVID-19 case in the last 14 days prior to onset of symptoms.
3. Subject is an appropriate candidate for Nasopharyngeal sample collection
4. Subject is willing to provide nasopharyngeal swab and saliva samples

#### 5.2 EXCLUSION CRITERIA

An individual who meets any of the following criteria will be excluded from participation in this study:

1. Individuals who present to ER with 10 or greater days of COVID-19 Related Symptoms, (Fever, Cough, Fatigue, Decreased Appetite, Shortness of Breath, Myalgia) or post-defervescence and/or convalescence

### 6 CONVALESCENCE.PARTICIPANT DISCONTINUATION/WITHDRAWAL

#### 6.1 DISCONTINUATION OF STUDY SAMPLE EVALUATION

Subjects may withdraw consent at any time and request that their samples not be processed.

## 7 STUDY ASSESSMENTS AND PROCEDURES

### 7.1 STUDY PROCEDURES

All reagents and DART viral transport media will be provided by the sponsor and shipped together. The dipsticks should be kept at Room Temperature until use.

1. Subjects will be approached by research staff to determine if they would be interested in participating in a study that requires an additional sample collection. If willing, then a qualified study team member will conduct the informed consent process with the subject, obtain verbal agreement by subject, document verbal consent of the participant, and provide a copy of the informed consent form information sheet to the participant.
2. Study staff will complete the necessary source document elements and case report forms collecting relevant subject demographic information, eligibility criteria, and medical history. Medical personnel will collect nasopharyngeal swabs (2X samples each), saliva, and serum.
3. One of the swabs will be utilized to conduct the traditional PCR method at the Hospital
4. The second nasopharyngeal swab collected in the 0.4ml viral E25Bio transport media
5. Mix vigorously and let stand until use within the next minutes
6. In a tube provided, apply the 100µl viral transport media
7. Insert dipstick for DART test into the tube.
8. The liquid should be moving up into the tests strip for minimum of 15 min and maximum of 30 minutes.
9. Visually read and interpret the final result as indicated below, two lines= positive. One line=negative and record on form.
10. A second DART swab may be administered if the results of the first swab are not interpretable.
11. Medical staff will collect saliva sample from participant for future use.

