8.4 STATISTICAL ANALYSES

8.4.1 GENERAL APPROACH

The 2X2 binary method is industry standard when testing a new clinical diagnostic with the gold standard. The positive and negative percent agreement between the candidate device results generated separately for each claimed matrix comparator method using 2 x 2 tables as follows:

	Clinical comparator method/Clinical truth (RT-PCR)		
		Positive	Negative
E25Bio Test	Positive	A	B
	Negative	C	D

Percent Positive Agreement =  $A/(A + C)$  or True Positives/(True Positives + False Negatives)

Negative Percent Agreement =  $D/(B + D)$  or True Negatives/(True Negatives + False positives)

---

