14.2 DART DIPSTICK VISUAL ASSESSMENT

Date of Dipstick Assessment (DD/MON/YYYY): / /

Check if not done	Protocol Timepoint	Time of Dipstick Assessment (HH:MM):	Result	If the assessment was not done, what was the reason?
	15 Minutes	  :  	 Positive for COVID-19 (Two lines on dipstick)  Negative for COVID-19 (One line on dipstick)  Inconclusive  No result assessment done	_____
	30 Minutes	  :  	 Positive for COVID-19 (Two lines on dipstick)  Negative for COVID-19 (One line on dipstick)  Inconclusive  No result assessment done	_____

If the assessment was inconclusive, was another sample collected?  Yes  No

Check if not done	Protocol Timepoint	Time of Dipstick Assessment (HH:MM):	Result	If the assessment was not done, what was the reason?
	15 Minutes	□□:□□	 Positive for COVID-19 (Two lines on dipstick)  Negative for COVID-19 (One line on dipstick)  Inconclusive  No result assessment done	_____
	30 Minutes	□□:□□	 Positive for COVID-19 (Two lines on dipstick)  Negative for COVID-19 (One line on dipstick)  Inconclusive  No result assessment done	_____ _____

**CP Note:** This form will not be displayed if the Sample Collection CRF indicates that no DART Nasopharyngeal Swab was collected.

Template: Custom

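### The DART reading rule counts lines without saying which one, so a strip with a failed control and a visible test line reads as negative

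*Protocol*

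**What the plan says.** Section 2.2 describes a dipstick printed with a capture antibody at the test line "and a control antibody (Control line) for quality control". A positive sample is one in which viral particles or spike protein "attach to both antibodies resulting in a visual line on the test strip within 15 minutes". The two lines therefore carry different information: the test line reports antigen, and the control line reports whether the strip worked.

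The reading rule in Section 7.1, step 9 does not use that distinction: "Visually read and interpret the final result as indicated below, two lines= positive. One line=negative and record on form". CRF 14.2 uses the same count in all four result cells (15 and 30 minutes, first and second sample), with the options "Positive for COVID-19 (Two lines on dipstick" and "Negative for COVID-19 (One line on dipstick", each followed by a closing bracket.

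Two provisions deal with unclear results. Step 10 says: "A second DART swab may be administered if the results of the first swab are not interpretable". CRF 14.2 has an Inconclusive box at each reading and then asks: "If the assessment was inconclusive, was another sample collected". Neither provision is linked to a line pattern or to the control line.

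The reading goes into the 2x2 table against RT-PCR in Section 8.4.1, from which PPA = A/(A + C) and NPA = D/(B + D) are calculated.

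**The concern.** The strip reading is one of the two inputs to the only endpoint, agreement with PCR. A control line matters only if its absence changes how the strip is classified, and here it does not. A strip showing only the test line satisfies the definition of a negative, although what is visible is the evidence for antigen and what is missing is the evidence that the strip is valid.

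In a PCR-positive subject, a strip ticked Negative this way enters cell C as a false negative. In a PCR-negative subject it enters cell D as a true negative. In both cases a Negative tick does not prompt the repeat swab that step 10 allows.

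An analysis rule cannot repair this afterwards. Once Negative is ticked, nothing on the form separates a test-line-only strip from a control-line-only strip.

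**Working it through.** **Step 1. Apply the written rule to every possible strip.** The two lines of Section 2.2 give four patterns.

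| Control line | Test line | Lines | Result under step 9 and CRF 14.2 | Meaning under Section 2.2 |
|---|---|---|---|---|
| seen | seen | 2 | positive | antigen detected, control worked |
| seen | absent | 1 | negative | no antigen detected, control worked |
| absent | seen | 1 | negative | antigen binding visible, control failed |
| absent | absent | 0 | not defined by the count; not negative | control failed |

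Only the third row is misclassified. Two-line strips are scored correctly, and strips with no line are not called negative.

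**Step 2. Size of the effect.** The protocol has no figure of its own to reproduce here. The inputs are n = 30 PCR-positive and n = 30 PCR-negative subjects (Sections 1.1 and 8.2) and the formulas in Section 8.4.1. For illustration, assume that one strip in the group is test-line-only at the reading that is analysed and is ticked Negative, and that all other strips agree with PCR. Intervals are Wilson 95%, with z = 1.96:

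(x + z²/2)/(n + z²) ± z/(n + z²) × √[x(n − x)/n + z²/4]

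For x = 29, n = 30: 30.92/33.84 ± (1.96/33.84) × √(0.967 + 0.960) = 0.914 ± 0.080, or 83.3% to 99.4%. When x = n the lower limit reduces to n/(n + z²): 30/33.84 = 88.6% and 29/32.84 = 88.3%.

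*PPA (strip in a PCR-positive subject).* As written, the strip is in cell C: 29/30 = 96.7% (83.3 to 99.4). If it were treated as invalid:

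| Outcome of the repeat swab | PPA | Change from as written |
|---|---|---|
| both lines | 30/30 = 100% (88.6 to 100) | +3.3 points |
| control line only | 29/30 = 96.7% (83.3 to 99.4) | 0 |
| invalid or not done, strip set aside | 29/29 = 100% (88.3 to 100) | +3.3 points |

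*NPA (strip in a PCR-negative subject).* As written, the strip is in cell D: 30/30 = 100% (88.6 to 100). If it were treated as invalid:

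| Outcome of the repeat swab | NPA | Change from as written |
|---|---|---|
| control line only | 30/30 = 100% (88.6 to 100) | 0 |
| invalid or not done, strip set aside | 29/29 = 100% (88.3 to 100) | 0 |
| both lines | 29/30 = 96.7% (83.3 to 99.4) | −3.3 points |

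**Step 3. Is 3.3 points the most that one strip can do to PPA?** Let A of the 30 PCR-positive subjects be scored positive as written. A repeat with both lines changes PPA by (A + 1)/30 − A/30 = 1/30 = 3.3 points, whatever A is. Setting the strip aside changes it by A/29 − A/30 = A/870, which is largest at A = 29, where it is 29/870 = 3.3 points. So the range per strip at n = 30 is 0 to 3.3 points, and it shrinks if more than 30 PCR-positive subjects are analysed.

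**The case against.** The strongest reply is that step 9 is shorthand and should be read with Section 2.2. On that reading, a strip without its quality-control line has failed, a trained reader would tick Inconclusive, and step 10 and the repeat block of CRF 14.2 already provide the route. That may well happen in practice. But the Inconclusive box and the step 10 condition are tied to no line pattern, while the one explicit rule sends a one-line strip to Negative. Readers can therefore differ, and the form would not show it.

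A reading guide might also exist elsewhere: step 9 speaks of an indication below, and Section 9.1.8 mentions a Manual of Procedures. This cannot be excluded, but the rule follows in the same sentence of step 9, and the form that is filled in repeats the line count.

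The remaining objections limit the size and are accepted. The pattern needs a failed control, a visible test line and a Negative tick together. Strips are read at 15 and 30 minutes, so one that is test-line-only at 15 minutes may show both lines at 30; it matters only if it is still test-line-only at the reading that is analysed. The documents give no control-failure rate, so no probability can be attached. The PPA error works against the device and cannot inflate PPA. The repeat swab is optional even after correct classification. How invalid strips enter the 2x2 table may properly be left to an SAP, but an SAP could not identify the strips already recorded as negative.

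**Conclusion.** The rule is wrong as written for one strip pattern, test line without control line, and the CRF carries the same error into the data. The severity is minor. At 30 PCR-positive subjects each affected strip lowers PPA by 0 to 3.3 points. NPA is unchanged unless a repeat would have shown both lines, in which case it is overstated by 3.3 points in the illustration. These figures assume that all other strips agree with PCR, that the strip is test-line-only at the analysed reading, and that the reader follows the literal rule. If no such strip occurs, or if readers tick Inconclusive, the effect is zero. This is a defect in the reading rule and the form, not a demonstrated bias in a result.

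**What to change.** In Section 7.1, step 9 and in every result cell of CRF 14.2, define the results by named lines:

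- positive: control line and test line both visible;
- negative: control line only;
- invalid: no control line, with or without a test line. Record it as Inconclusive and count it as not interpretable under the existing step 10.

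Add a yes/no box for a visible control line at each reading on CRF 14.2, so that the classification can be checked from the data.

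The cost is one sentence in Section 7.1, matching CRF labels and one extra box per reading. A few strips may move from negative to invalid, so the evaluable number may fall slightly, and a few more of the second swabs that step 10 already allows may be used.

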8.3 POPULATIONS FOR ANALYSES

Subjects testing positive or negative by PCR and having DART assessments

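### Repeating a non-interpretable DART strip is left to staff discretion, and the 2x2 formulas have no place for a failed strip, so repeats can be selective and failures need not show in PPA or NPA

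*Protocol*

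**What the plan says.** Section 7.1, step 9 gives two outcomes for the strip: "two lines= positive. One line=negative and record on form". Step 10 then adds: "A second DART swab may be administered if the results of the first swab are not interpretable". It does not define a non-interpretable result, require the repeat, or say which result counts afterwards.

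The schema in section 1.2 ends with the instruction "Collect readings after 15 and after 30 minutes". The case report form, section 14.2, follows this with one line for each time, and each line offers Inconclusive as a result. Below them it asks "If the assessment was inconclusive, was another sample collected", and a second pair of 15- and 30-minute lines follows. No field names the final DART result.

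Section 8.3 defines the analysis population as "Subjects testing positive or negative by PCR and having DART assessments". Section 8.4.1 sets out a table with cells A, B, C and D, DART positive or negative against PCR positive or negative. Positive agreement is A/(A + C) and negative agreement is D/(B + D). For further analysis details, section 8 points to an FDA guidance document.

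**The concern.** Three features act together. First, the decision to take a fresh swab after a failed strip is made case by case, by staff who may know the patient's history and symptoms; step 2 of section 7.1 has study staff record these. Second, the trigger is loose. Step 9 has no category for a failed strip and sets no control-line condition, although section 2.2 describes a control line for quality control. The form's question also does not say whether a strip that is inconclusive at 15 minutes but clear at 30 counts as inconclusive. Third, neither formula has a term for a failed strip.

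Two things are at stake. If some failed strips are repeated and others are not, the subjects who contribute a usable result may be a selected group, and no later analysis can supply the repeats that were never taken. In addition, the product is meant to give a quick result at the point of care. A strip that cannot be read does not do that, yet the primary endpoint can be reported without showing how often it happened.

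**Working it through.** **The plan's own figure.** Section 8.2 sets 30 positive and 30 negative samples. It gives no confidence level, target agreement or precision, so the figure cannot be reproduced. It is not disputed here and serves only as the column size.

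**Inputs.** Column size n = 30 (section 8.2). Agreement = A/(A + C) in the PCR-positive column or D/(B + D) in the PCR-negative column (section 8.4.1); the arithmetic is the same for both. The number of non-interpretable first strips, k, is not given in the protocol. It is assumed to be 1, 3 or 6 of 30. Intervals are exact (Clopper-Pearson) 95%.

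**Handlings compared.**
- Dropped: failed strips leave numerator and denominator, (30 − k − f)/(30 − k), where f is the number of interpretable strips that disagree with PCR.
- Replaced by agreeing repeats: (30 − f)/30.
- Counted as disagreement: (30 − k − f)/30.

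**Case f = 0, all interpretable first strips agree.**

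| k | Dropped (lower limit) | Replaced, repeats agree (lower limit) | Counted as disagreement (95% CI) |
|---|---|---|---|
| 1 | 29/29 = 100% (88.1%) | 30/30 = 100% (88.4%) | 29/30 = 96.7% (82.8 to 99.9) |
| 3 | 27/27 = 100% (87.2%) | 30/30 = 100% (88.4%) | 27/30 = 90.0% (73.5 to 97.9) |
| 6 | 24/24 = 100% (85.8%) | 30/30 = 100% (88.4%) | 24/30 = 80.0% (61.4 to 92.3) |

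The point estimates in the first two columns are higher than in the last by 3.3, 10.0 and 20.0 points. Each failed strip is worth 1/30 = 3.3 points.

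**Case f = 3, k = 3.** Dropped: 24/27 = 88.9%. Replaced by agreeing repeats: 27/30 = 90.0%. Counted as disagreement: 24/30 = 80.0%.

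**Two checks on the reading of these figures.**
- Dropping and replacing by agreeing repeats lie close together: 90.0 − 88.9 = 1.1 points in the last case, and no difference when f = 0. The large gaps arise only against counting a failed strip as disagreement.
- If all the repeats disagree with PCR and are used, the result equals the last column: 24/30 = 80.0% for k = 3, f = 3. Replacement is therefore not favourable by construction; that depends on what the repeats show.

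**The case against.** A reader might infer that the plan inflates PPA and NPA, and by about 10 points. The documents do not support that, for these reasons.

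- Step 10 permits a repeat only after a non-interpretable result. A clear result that disagrees with PCR gets no second chance under the text.
- Section 5.1 requires every subject to be a clinically suspected case, so suspicion alone separates subjects less than it would in a mixed population. Section 2.1 says PCR can take hours to days, so the PCR result will often be unknown when the strip is read.
- If failures are unrelated to true status, agreement among interpretable strips is unbiased.
- The gap of 10 points rests on an assumed 3 failures in 30 and on a benchmark the protocol does not adopt. Cell C holds DART-negative results, not failed strips.
- Nothing says that a failed strip is dropped. A subject with an inconclusive strip could be read as having a DART assessment under section 8.3. The form keeps the first-strip readings beside the repeat, so the failure rate can be recovered.
- Which reading enters the table is commonly fixed in a statistical analysis plan, and that plan is not at hand.

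All of this stands as a limit on direction and size. It does not remove the point. The optional repeat is a data-collection rule stated in the protocol, and an analysis plan cannot restore repeats that were not taken. The undefined trigger also sits in the protocol and its form. The form keeps the failures, but no section requires them to be reported.

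**Conclusion.** The point holds as a weakness that allows bias, not as a demonstrated bias. As written, repeats can be selective, and PPA and NPA can be reported without the failed strips. This can favour the test but is not shown to do so. Even in the benign case, with failures unrelated to true status, the failure rate stays hidden.

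The size depends on an unknown failure rate. With every interpretable strip agreeing with PCR in a column of 30, 1 to 6 failed first strips separate 100% from 96.7% down to 80.0%, according to whether failures are left out of the figure or counted against the test. These are assumed inputs, and the comparison is with a deliberately strict benchmark.

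Whether the first strip or the result after a repeat should be primary is a choice on which statisticians may differ. What should not stay open is who gets a repeat, and on which reading.

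**What to change.** 1. In section 7.1, step 10, replace the optional wording with one uniform rule that applies to every subject whose first strip is non-interpretable at one named read, whatever the clinical impression. Define non-interpretable there.
2. In section 14.2 of the case report form, tie the question about another sample to that same read.
3. Name in advance the DART result that enters the 2x2 table in section 8.4.1.
4. Report the number of non-interpretable first strips by PCR status, from data the form already collects.
5. Add a sensitivity analysis that counts those strips as disagreement.

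The cost is a wording change in the protocol, one clarification on the form, a few more repeat swabs, one extra table and a possibly less favourable figure.
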